8.2 Background and demographic characteristics

Demographics and baseline characteristics will be presented for FAS. Data already collected for core study will be presented for the extension analysis subjects as well.

The following common background and demographic variables will be analyzed according to the treatment sequence.

Continuous variables:

- Age (which is derived from date of birth and the screening assessment date)
- Height
- Weight
- Body mass index (BMI) = (body weight in kilograms) / (height in meters)²

Categorical variables:

- Age categories (<65 years, 65 years and older, 75 years and older)
- Gender
- Race
- Ethnicity
- Weight (<90 kg or ≥90 kg)
- Smoking status at baseline

The following disease specific baseline characteristics and history of disease will be summarized as well:

CASPAR, TNF- α history (naive or inadequate responder), ACR components, number of prior biologic PsA therapies, MTX use (yes or no) and dose at baseline, time since first diagnosis of PsA in years, and psoriasis involvement (proportion of patients with psoriasis of hands and feet, psoriasis of the nail, and target lesion diameter, psoriasis \geq 3% of BSA), DAS28 CRP and DAS28 ESR scores, HAQ-DI, [REDACTED] and systemic use of glucocorticoids.

Unless otherwise specified, summary statistics for continuous variables will be presented for each treatment group, for each placebo-AIN457 group, for the combination of AIN457 and

placebo switchers and finally for all subjects (total) in the FAS. The number and percentage of subjects in each category will be presented for categorical variables for each treatment group and all subjects (total) in the FAS.

9 Medical history

Any condition entered on the *Relevant medical history / current medical conditions* CRF will be coded using the MedDRA dictionary. Data collected for core study will be used for the extension as well. Data will be summarized by system organ class (SOC) and preferred term (PT) of the MedDRA dictionary. Summaries for cardiovascular medical history and psoriasis history will be provided as well. Disease history and baseline characteristics will be presented by treatment group.

Smoking history will be summarized by treatment sequence.

Disease history will be displayed by treatment sequence. Unless otherwise specified, analyses will be based on the extension FAS.

10 Study medication

The analysis of study treatment data will be based on the safety set. The number of active injections will be summarized by treatment received. The duration of exposure to study treatment will also be summarized by treatment received. In addition, the number and percentage of subjects with cumulative exposure levels (e.g. any exposure, ≥ 1 week, ≥ 2 weeks, ≥ 3 weeks, ≥ 4 weeks, ≥ 8 weeks, etc.) will be presented.

Duration of exposure will be calculated as time from first dose of secukinumab in core to the minimum of (last dose of the treatment + 84 days) and (last visit date). For subjects who discontinue, this will be the subject's last visit in the corresponding treatment period.

Duration of exposure (years) = duration of exposure (days) / 365.25

Duration of exposure (100 subject years) = duration of exposure (years) / 100

The analyses of duration of exposure described above will be done for the entire study treatment period.

11 Concomitant medication

Concomitant medication in extension

Concomitant medications in extension will be summarized by treatment received. Any medication given at least once between the start of the first dose in this extension trial and the date of the last study visit + 84 days in the extension study, will be a concomitant medication,

including those which were started before Week 104E1 and continued into the extension study where study treatment is administered.

Medications will be presented in alphabetical order, by Anatomical Therapeutic Classification (ATC) codes and grouped by anatomical main group. Tables will show the overall number and percentage of subjects receiving at least one treatment of a particular ATC code and at least one treatment in a particular anatomical main group.

Significant concomitant non-drug therapies and procedures will be summarized by primary system organ class and MedDRA preferred term.

Prior surgeries and procedures are defined as surgeries and procedures executed prior to the first study dose. Any surgeries and procedures started between the day of the first dose of study treatment and within 84 days after the last dose will be concomitant surgeries and procedures, including those which were started pre-baseline and continued into the period where study treatment is administered.

The number and percentage of subjects receiving prior and concomitant psoriatic arthritis therapy will be presented by treatment group as well as the reasons for stopping their therapies (primary lack of efficacy, secondary lack of efficacy, lack of tolerability, other) and the total duration of exposure to psoriatic arthritis therapies previously.

Concomitant medication in core or extension

Concomitant medications data collected in core and extension will be combined together. Data for concomitant medications for core are collected in core study and the same will be used.

Any medication given at least once between the start of the first dose in core trial and the date of the last study visit in the extension trial will be summarized. Data will be analyzed on safety set.

Prior or concomitant medication will be identified by comparing recorded or imputed start and end dates of medication taken to the reference start date.

Further rules will be given in PDS.

12 Efficacy evaluation

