13.11 Appendix 11: Study design of core study CAIN457F2306

The AIN457F2306 core study used a double-blind, randomized, parallel-group, placebo controlled design. A screening period running 4 weeks before randomization was used to assess eligibility followed by a treatment period of 2 years (Week 0 through Week 104).

At baseline (BSL), eligible subject were randomized to one of three treatment groups:

- Group 1: Secukinumab i.v. (10mg/kg) at BSL, Weeks 2 and 4, then secukinumab 75 mg s.c. starting at Week 8 and injected every 4 weeks
- Group 2: Secukinumab i.v. (10mg/kg) at BSL, Weeks 2 and 4, then secukinumab 150 mg s.c. starting at Week 8 and injected every 4 weeks
- Group 3: Placebo i.v. at BSL, Weeks 2 and 4, then placebo s.c. starting at Week 8 and Week 12

The subjects were stratified as either TNF α inhibitor incomplete responders (TNF-IR) or TNF α inhibitor naïve subjects. Approximately 30% of subjects were TNF-IR to ensure a representative population for the assessment of efficacy and safety.

At Week 16 (Visit 8), subjects were classified as responders ($\geq 20\%$ improvement from baseline in both tender and swollen joint counts) or non-responders. Subjects who were randomized to placebo at baseline were re-randomized by IRT to receive double blind treatment up to 2 years, as follows

- Subjects on secukinumab placebo (Group 3) who were responders remained on placebo until week 24. At Week 24, these subjects were re-randomized (1:1) to receive either secukinumab 75 or 150 mg every 4 weeks
- Subjects on secukinumab placebo (Group 3) who were non-responders at Week 16 were re-randomized (1:1) to receive either secukinumab 75 mg or 150 mg s.c. every 4 weeks

Figure 13-1 Core Study (CAIN457 F2306) Design

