5.1 Treatment groups

The arms included in efficacy tables are based on the treatment sequence (picturing also the up-titration) for the periods up to the final lock at week 260. Two separate columns will display the assigned and actual treatment resulting in the following treatment sequences:

Efficacy:

- AIN457 10 mg/kg - 75 mg
- AIN457 10 mg/kg - 75 mg - 150 mg
- AIN457 10 mg/kg - 75 mg - 300 mg
- AIN457 10 mg/kg - 150 mg
- Placebo - AIN457 75 mg
- Placebo - AIN457 75 mg - 150 mg
- Placebo - AIN457 75 mg - 300 mg
- Placebo - AIN457 150 mg

After week 52 the combination of assigned treatment will also be shown.

- AIN457 75 mg & Placebo - AIN457 75 mg
- AIN457 150 mg & Placebo - AIN457 150 mg

The treatment sequence following up-titration for the combined groups will be:

- AIN457 75 mg & Placebo - AIN457 75 mg - 150 mg
- AIN457 75 mg & Placebo - AIN457 75 mg - 300 mg
- AIN457 150 mg & Placebo - AIN457 150 mg – 300 mg

Cases might up-titrate twice; for these cases the treatment prior to each up-titration will be displayed (that is not the assigned treatment for the 2nd observed up-titration). Therefore, at the graphical representation of up-titration the actual treatment dose prior to the switch will be displayed.

Regarding safety, the arms included in the entire treatment period are as follows.

- Any AIN457 75 mg
- Any AIN457 150 mg
- Any AIN457 300 mg
- Any AIN457 (if appropriate)

Placebo group will be included at the in-text tables and listings of the CSR.

In the safety listings the groups will be the following:

- AIN457 10 mg/kg - 75 mg
- AIN457 10 mg/kg - 150 mg
- Placebo AIN457 75 mg
- Placebo AIN457 150 mg
- Placebo not re-randomized.

6 Subgroup definitions

The primary endpoint and secondary endpoints will be evaluated for TNF-alpha inhibitor status and by concomitant MTX use (ACR20/50, [REDACTED]).

7 Assessment windows, baseline and post baseline definitions, missing data handling

Baseline and post-baseline definitions

In general, a *baseline* value refers to the core study and is the last measurement made prior to administration of the first dose of study treatment in core. Baseline information will be presented appropriately in the “by visit” summaries in both safety and efficacy tables.

A post-baseline value refers to a measurement taken after the first dose of study treatment in core study.

Analysis visit windows

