13.1 Pharmacokinetics

All completed subjects with quantifiable pharmacokinetic (PK) measurements of secukinumab will be included in the pharmacokinetic data analysis. Serum concentrations will be expressed in mass per volume units. All concentrations below the limit of quantification as well as missing data will be labeled as such in the concentration data listings. PK concentrations will be summarized by visit and treatment group. In addition to mean, standard deviation (SD), coefficient of variation (CV), median and quartiles, the geometric mean and geometric coefficient of variation (CV) and n(log) will be presented. The formula for deriving the geometric mean and CV (%) is as following:

- $CV (\%) = (SD/mean) * 100$,
- $geometric\ mean = \exp(\text{sum of log transformed data} / \text{number of non-missing data points after log transformation})$,
- $geometric\ CV = \sqrt{\exp(\text{variance of log-transformed data}) - 1} * 100$.

In addition, sample number, concentration, sample date, sample time at pre-dose and minutes pre-dose will be listed by treatment sequence.

Values below lower limit of quantification/below detection limit will be imputed by 0.

Pharmacokinetic data of the study treatment will be analyzed with a population-pharmacokinetic mixed effects model. The analysis will be based on a pooled data set, including pharmacokinetic samples from previous studies. The modeling approach will be further detailed in a modeling plan. Results will be reported separately.

14 Safety evaluation

Safety analyses will be done on the safety set.

Summaries will be presented cumulatively from core and extension. For subjects who switched from placebo to secukinumab in core, their data prior to switch will only be reported in in-text tables and listings.

Safety analyses will be performed on treatment received or actual treatment as described below:

The actual treatment or treatment received for summaries of safety data will differ to the treatment assigned at randomization if a subject received the wrong treatment during the core and extension study or if the subject up-titrated to a higher dose.

Subjects who switch treatment during the study (e.g. from placebo to active treatment, or had dose escalation) will be counted to both groups using the appropriate start and stop exposure date.

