17.3.4 Exposure adjusted incidence rate and related risk estimates

17.3.4.1 Exposure adjusted incidence rate and 100*(1-α)% confidence interval

It will be assumed that for each of n subjects in a clinical trial the time t_j ($j=1, \dots, n$) to the first occurrence of a certain event is observed, or if the event was not experienced, the (censored) time to the end of the observation period. The sequence of first occurrences of an event will be modeled to follow approximately a Poisson process with constant intensity θ . The rate

parameter θ will be estimated as $\lambda=D/T$, where $T = \sum_{j=1}^n t_j$ and D is the number of subjects with

at least one event. Conditionally on T , an exact 100*(1-α)% confidence interval for a Poisson variable with parameter θT and observed value D can be obtained based on (Garwood, 1936),

from which an exact $100*(1-\alpha)\%$ confidence interval for D/T will be derived as follows (Sahai, 1993; Ulm, 1990):

$$\text{Lower confidence limit } L = \frac{0.5c_{\alpha/2, 2D}}{T} \text{ for } D > 0, 0 \text{ otherwise,}$$

$$\text{Upper confidence limit } U = \frac{0.5c_{1-\alpha/2, 2D+2}}{T}$$

where $c_{\alpha, k}$ is the α th quantile of the Chi-square distribution with k degrees of freedom.

The example below shows how this should be handled for cases where subjects switch treatment. In particular for summarizing ‘Any AIN’ as a group, one should take into consideration the sequence of treatments while calculating exposure time for subjects.

Table 17-3 Examples for calculating exposure time for incidence rates (IR)

1st treatment	1st exposure	2nd treatment	2nd exposure	Event days (in terms of study day)	Exposure for IR
Placebo	100 days	150 mg	200 days	50 (1st trt) 110 (10 days into 2nd trt)	Placebo: 50 days (event) 150 mg: 10 days (event) Any AIN: 10 days (event)

18 References

[REDACTED]

[REDACTED]

[REDACTED]

[REDACTED]

[REDACTED]

[REDACTED]

[REDACTED]

[REDACTED]

AIN457A efficacy MAP M3, available in Cabinets//CREDI Projects/A/AIN457A /Administrative files/CIS (Clinical Information Sciences)/Biostatistics

AIN457 safety MAP M3, available in Cabinets//CREDI Projects/A/AIN457A/Administrative files/CIS (Clinical Information Sciences)/Biostatistics

Biostatistical Guidance on Analysis Sets in Clinical Trials, available in Cabinets/CREDI TABULU/B&SR/CIS Process Documentation/Guidances (outside of ESOPS)/Others

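### SAP Section 10 starts every exposure clock at the first secukinumab dose in the core study, so the 300 mg column is overstated for every escalated subject

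*SAP*

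**What the plan says.** SAP Section 10 (Study medication), on the safety set, states: "The duration of exposure to study treatment will also be summarized by treatment received". It then gives one definition: "Duration of exposure will be calculated as time from first dose of secukinumab in core to the minimum of (last dose of the treatment", to which 84 days are added, and the last visit date, whichever comes first. For subjects who discontinue, the end is the "last visit in the corresponding treatment period". The section applies this to the entire treatment period and converts the result to units of 100 subject-years.

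SAP Section 5.1 sets the safety columns as Any AIN457 75 mg, 150 mg and 300 mg, plus Any AIN457 where appropriate. The column at issue is "Any AIN457 300 mg".

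Two other places deal with subjects who change treatment:

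- SAP Section 14 says that up-titration changes the treatment received. For subjects who switch, its operative words are "or had dose escalation) will be counted to both groups using the appropriate start and stop exposure date". It does not say what those dates are.
- SAP Section 17.3.4.1, on incidence rates, says "The example below shows how this should be handled for cases where subjects switch treatment" and, for the Any AIN group in particular, that "one should take into consideration the sequence of treatments while calculating exposure time for subjects". The only example, in Table 17-3, is a subject going from placebo to 150 mg.

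**The concern.** Section 10 is right for Any AIN457 and for subjects who never escalate: it keeps the intravenous loading period in and placebo time before the switch out. It fails for a subject who changes dose level. 300 mg was neither a core regimen nor a starting dose in the extension, so on the planned schedule everyone in the 300 mg column is an escalator. Read as written, each brings to that column all secukinumab time since the core study.

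The lower-dose column is affected too, at its end. If the last dose of the treatment means the last secukinumab dose, that column runs to the end of the study. If it means the last dose at that level, the 84-day tail runs past escalation and overlaps the time at the higher dose.

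The by-dose exposure table tells readers how much long-term experience the study provides at each dose. Overstating it for 300 mg would misdescribe the evidence. If the same durations became rate denominators, 300 mg event rates would look too low.

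**Working it through.** **Inputs**

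- No dose adjustment before Week 156 (Protocol 3.1 and 5.5.5).
- Escalation may be decided at any on-site visit, with no later reduction (Protocol 5.5.5).
- Last dose at Week 256, final visit F268 (Protocol 5.5.11).
- First secukinumab dose at Week 0, or at Week 16 or 24 for subjects who began on placebo (Protocol Appendix 11).
- Dosing every 4 weeks.

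**The SAP's own example.** Table 17-3 has 100 days of placebo, then 150 mg, with events on study days 50 and 110. Placebo exposure is 50 days; 150 mg exposure is 110 − 100 = 10 days; Any AIN is 10 days. All three entries reproduce. In this row the switch is also the first secukinumab dose, so the two secukinumab entries come out the same whether the clock starts at the switch or at first secukinumab. The row does not settle a change from one secukinumab dose to another.

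**Bounds for the 300 mg column**

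- End of exposure for a completer: Week 256 + 84 days = Week 268, which is also the last visit.
- Most that can be true: 268 − 156 = 112 weeks.
- Least that the written rule can give, even if the subject stops right after the first 300 mg dose: 156 − 24 = 132, 156 − 16 = 140, or 156 − 0 = 156 weeks, by first secukinumab week.

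The smallest value the rule can produce exceeds the largest true value, however many subjects escalated and whenever they did.

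**Completers, by escalation week.** The rule gives 268, 252 or 244 weeks for starts at Week 0, 16 or 24. The documents do not say when escalations took place, so a range of scheduled on-site dosing visits is shown.

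| Escalation to 300 mg | True weeks at 300 mg | Ratio, Week 0 start | Week 16 start | Week 24 start |
|---|---|---|---|---|
| Week 156 | 112 | 2.39 | 2.25 | 2.18 |
| Week 180 | 88 | 3.05 | 2.86 | 2.77 |
| Week 208 | 60 | 4.47 | 4.20 | 4.07 |
| Week 244 | 24 | 11.17 | 10.50 | 10.17 |

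Per 100 Week 0 starters escalated at Week 156: 100 × 268 × 7 / 365.25 = 513.6 subject-years, against 100 × 112 × 7 / 365.25 = 214.6.

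**Lower-dose column.** With the last lower dose 4 weeks before escalation, the tail overlaps the higher dose by 84 − 28 = 56 days. Take a Week 0 starter moved from 75 to 300 mg at Week 180, whose total exposure is 268 weeks. The two columns sum to 268 + 268 = 536 weeks if the treatment means secukinumab overall, or (176 + 12) + 268 = 456 weeks if it means the dose level.

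**Rates, only if the interval were reused.** For a rare event and escalation at Week 156, the displayed 300 mg rate would be 112 / 268 = 0.42 of its true value.

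**The case against.** The best defence is that Sections 10 and 14 share the term treatment received and should be read together. Section 14 names dose escalation and calls for dates specific to each group, so the specific rule qualifies the general formula. Table 17-3 supports this: its placebo entry of 50 days cannot come from a clock that starts at first secukinumab, and it stops first-treatment exposure where the second begins. On that view a careful programmer would split correctly, and only a cross-reference is missing. Further detail may also sit in programming specifications not available here.

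Much of this stands. The intended split is clear, the rate section points the right way, and nothing shows that the rates will be wrong. With no count or timing of escalations, no actual column total can be estimated. The tables are descriptive, no hypothesis is tested, and efficacy is untouched.

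It does not clear Section 10, which is not silent: it states a start date, and that date is wrong for every 300 mg recipient. Section 14 contradicts it without supplying a replacement. The SAP refers to the programming specifications for concomitant medication and for adverse event date imputation, not for exposure.

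**Conclusion.** The point holds and should be fixed. Applied as written, Section 10 gives at least 132 weeks of 300 mg exposure to subjects who can have at most 112, and conflicts with Section 14. For completers the overstatement is at least 2.2-fold, and 2.4-fold for a Week 0 starter escalated at Week 156. These figures assume the planned visit schedule with uninterrupted dosing; escalation weeks other than the earliest possible are illustrative. The effect is limited to by-dose exposure duration and the cumulative-exposure categories. The factor of 0.42 on rates applies only if the Section 10 interval is carried into Section 17.3.4.1, which Section 14 suggests is not intended but which no defined interval prevents.

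**What to change.** In SAP Section 10:

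- Keep the present formula for Any AIN457.
- Start the initial subcutaneous dose column (75 or 150 mg) at the first secukinumab dose in core, and count the loading doses in that column. The protocol's Group 1 regimen, for example, was "Secukinumab i.v. (10mg/kg) at BSL, Weeks 2 and 4, then secukinumab 75 mg s.c. starting at Week 8 and injected every 4 weeks"; starting at the first 75 mg dose instead would leave Weeks 0 to 8 in no dose column.
- Start each escalated-dose column at the first dose at that level.
- Stop each column at the earliest of the day before the first dose at the next level, the last dose at that level plus 84 days, and the last visit. Retain the existing rule for discontinuation.
- Count days as stop − start + 1.
- Add a sentence on how a one-off administration of a wrong dose is allocated, since Section 14 recognises that case and the blocks above assume planned dosing.

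Cite these intervals in Sections 14 and 17.3.4.1, and add a 75–150–300 mg row to Table 17-3.

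Because no dose reduction is allowed, each level is one planned block, and with uninterrupted dosing the dose columns must sum to Any AIN457. That gives a programming check, with Day 1 as the first secukinumab dose for a Week 0 starter and a completer total of 268 × 7 + 1 = 1877 days:

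- Escalation at Week 180: 1260 + 617 = 1877.
- 75–150–300 mg at Weeks 156 and 208: 1092 + 364 + 421 = 1877.
- Discontinuer escalated at Week 156, last dose Week 180, last treatment-period visit Week 184: 1092 + 197 = 1289, equal to the Any AIN457 total.

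The cost is SAP wording and exposure-dataset programming. No new data are needed: Protocol 5.5.4 already requires dose changes to be entered on the Dosage Administration Record eCRF.

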For all subjects who discontinue or withdraw from the study, the investigator should ensure that the subject completes an end of treatment visit (corresponding to the last visit for the subject's current period of treatment) 4 weeks after last study treatment, and also returns after an additional 8 weeks for a final follow-up visit (12 weeks after last study treatment, see [Table 6-1](#), [Table 6-2](#) and [Table 6-3](#)). The final visit should be performed before any new treatment is initiated.

Lost to follow-up

For subjects who are lost to follow-up (i.e. those subjects whose status is unclear because they fail to appear for study visits without stating an intention to withdraw), the investigator should show "due diligence" by documenting in the source documents steps taken to contact the subject, e.g. dates of telephone calls, registered letters, emails etc.

Replacement

Subjects who are prematurely withdrawn from the study will not be replaced.

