5.5.12 Early study termination

The study can be terminated at any time for any reason by Novartis. Should this be necessary, the subject should be seen as soon as possible and treated as a prematurely withdrawn subject. The investigator may be informed of additional procedures to be followed in order to ensure that adequate consideration is given to the protection of the subject's interests. The investigator will be responsible for informing IRBs and/or ECs of the early termination of the trial.

6 Visit schedule and assessments

Table 6-1, Table 6-2 and Table 6-3 list all of the assessments and indicate with an "X" when the visits are performed.

Subjects should be seen for all visits on the designated day or as close to it as possible. Subjects should not receive study medication within less than 2 weeks after the previous administration.

During the treatment periods, subjects may be seen at an unscheduled visit, e.g. if they experience deterioration of their condition, or AEs that in the opinion of the investigator need intervention or repeated laboratory testing. During these unscheduled visits, study treatment will not be administered. Subjects who discontinue study treatment will continue to be followed for safety assessments. They are not considered withdrawn from the study.

Subjects who discontinue study treatment before completing the study, and those who prematurely withdraw from the study for any reason should be scheduled for a study visit 4 weeks after their last study treatment administration, at which time all the assessments listed for EoT for the given treatment period (Week 156 or 208 or 260) will be performed (see [Section 5.5.9](#)). Subjects will then return to the study site 12 weeks after the last study treatment administration for further assessments as indicated under the follow-up visits (F268).

If they refuse to return for these assessments or are unable to do so, every effort should be made to contact them or a knowledgeable informant by telephone or by sending appropriate correspondence (i.e. certified letter) immediately. At this contact, the safety (e.g., potential occurrence of AE or SAE) and the primary reason for a subject's premature withdrawal should be determined.

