14.1 Adverse events

The crude incidence of treatment emergent adverse events on secukinumab (i.e. events started after the first dose of secukinumab in core study or events present prior to the first dose of secukinumab but increased in severity based on preferred term and within 84 days after last dose of secukinumab) will be summarized by primary system organ class and preferred term for the entire treatment period. Confidence intervals for the crude rate will be derived as described in Section 17.2.3.1 In addition, exposure time-adjusted rates (incidence rate) including 95% confidence intervals will be provided for selected terms for the entire treatment period, (see Section 17.2.4.1) to adjust for differences in exposure.

Adverse events reported will be presented in descending frequency according to its incidence in total secukinumab group (combining all secukinumab treatment groups) starting from the most common event.

Summary statistics will be provided by primary system organ class and preferred term for the entire treatment period for all TEAEs, for serious TEAEs, for possibly related TEAEs, for deaths, for TEAEs causing treatment discontinuation, other serious or clinically significant treatment emergent adverse events or related discontinuations, for TEAEs leading to temporary dose interruptions, for SPP risks and for adjudicated major adverse cardiovascular events (MACE). Separate summaries for adverse events suspected to be related to study drug, will also not be displayed in the current analysis.

TEAEs will also be summarized by primary system organ class and preferred term for the entire treatment period in time segments of 52 and 26 weeks.

Summaries (crude incidence only) will be presented for TEAEs by maximum severity as well. If a particular AE 'severity' is missing, this variable will be listed as missing and treated as missing in summaries.

If a subject reported more than one adverse event with the same preferred term, the adverse event with the greatest severity will be presented. If a subject reported more than one adverse event within the same primary system organ class, the subject will be counted only once with the greatest severity at the system organ class level, where applicable.

When adjudication is required of major cardiovascular events, a summary of those types of events as reported by the investigator and confirmed by adjudication will be provided.

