Exposure adjusted incidence rates for TEAEs, selected lower lever risk terms based on TEAEs, serious adverse events, adverse events leading to discontinuation, common AEs (frequency >2% in the Any AIN457 group during the first 24 weeks of treatment or IR > 5/100 subject years during the entire treatment period), SPP risks and MACE will be summarized by primary system organ class and/or by preferred term for the entire period.

The incidence of AEs will be presented per 100 subject years of exposure.

Exposure adjusted incidence rates for TEAEs will also be provided for specific common or very common TEAEs (very common TEAEs are described in the Core Data Sheet).

Adverse events will be reported separately by SMQ according to MedDRA. The MedDRA version used for reporting will be described in a footnote.

Algorithms for date imputations will be provided in the PDS.

The safety analyses that will be performed for treatment emergent AEs, labs, ECG and vital signs for each analysis period is described in table below.

Listings will be provided for all adverse events, all non-fatal serious adverse events, deaths, adverse events leading to discontinuation from study treatment or temporary dose interruption, adverse events by SPP risks and adjudicated MACE events (myocardial infarctions, strokes, and cardiovascular deaths).

For SAEs that occurred during screening a listing will be prepared for all subjects screened including screening failures.

No graphical displays of the crude incidence rates and exposure-adjusted rates will be presented for any AEs and serious AEs by system organ class in the current interim analysis.

An overview of the safety analyses and which will be performed for each analysis period is described in [Table 14-1](#).

Table 14-1 Overview of analyses on some safety endpoints

Analysis period	AEs & SAEs	AEs by severity	Study drug related AEs	AEs-SMQ	Risk	Notables for (vitals/ ECG), lab criteria
Entire Treatment	
 •crude incidence •exposure time adjusted incidence* 	
 •crude incidence 	
 •crude incidence 	
 •exposure time adjusted incidence 	
 •crude incidence •exposure time adjusted incidence 	
 •crude incidence

*Exposure-adjusted incidence rates will be done for the following:

- at the PSOC for AE and SAE

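### For subjects who discontinue, SAP Section 10 stops exposure about 4 weeks after last dose while adverse events count to 84 days; if that exposure is the rate denominator, incidence rates are biased slightly upward

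*SAP*

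**What the plan says.** **Exposure.** SAP Section 10 (Study medication) runs exposure from the first secukinumab dose in the core study to the earlier of 84 days after last dose and the last visit date. For subjects who discontinue, the next sentence replaces this end date with the "last visit in the corresponding treatment period". The same section converts duration into units of 100 subject-years.

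**Visit timing.** Protocol 5.5.9 has subjects who discontinue or withdraw complete an end-of-treatment visit, described in very similar words: "last visit for the subject's current period of treatment) 4 weeks after last study treatment". Protocol Section 6 agrees: such subjects are "scheduled for a study visit 4 weeks after their last study treatment administration". The later visit is separate, a "final follow-up visit (12 weeks after last study treatment", and Table 6-3 puts Week 268 in its own post-treatment epoch.

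**Events.** SAP 14.1 counts treatment-emergent events that fall "within 84 days after last dose of secukinumab", with no exception for discontinuers.

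**Rates.** SAP 14.1 states: "The incidence of AEs will be presented per 100 subject years of exposure". SAP 17.3.4.1 estimates the rate as D/T. D is the number of subjects with at least one event. T sums each subject's time to first event or, for event-free subjects, to an end of observation that the SAP does not define.

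**The concern.** A rate is interpretable when events and time at risk cover the same period. Read as written, a discontinuer's first event between days 29 and 84 after last dose enters D, but a discontinuer who stays event-free over those days adds no time from them to T. The mismatch works in one direction, and completers are not affected.

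Long-term safety is a secondary objective, and exposure-adjusted rates with exact Poisson limits are a main safety summary. The rates and their limits would be somewhat too high, and by different amounts in dose columns that differ in discontinuation or in length of exposure.

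**Working it through.** **1. The plan's own example.** SAP Table 17-3 is the only worked figure on the denominator. An event on day 50 gives placebo 50 days. An event on day 110, after 100 placebo days, gives 110 − 100 = 10 days for 150 mg and 10 for any secukinumab. The figures reproduce, but every entry ends in an event, so the table does not show where an event-free subject is censored.

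**2. Completers.** Last dose is at Week 256 and follow-up at Week 268: (268 − 256) × 7 = 84 days. Exposure and event windows match.

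**3. Discontinuers.** Exposure ends at 4 × 7 = 28 days after last dose and events count to day 84. The gap is 84 − 28 = 56 days, and 56 / 365.25 = 0.153 year. The result is the same whether the discontinuer sentence replaces the whole rule or only its last-visit term.

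**4. Are events in the gap collected?** Yes. Protocol 7.2 requires serious events to be reported for at least 12 weeks after last dose. Protocol Section 6 requires safety contact over those 12 weeks, with a final contact at the 12-week point.

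**5. Other windows in the SAP.** Sections 14.2 to 14.4 take laboratory, vital sign and ECG data as on-treatment up to last dose + 84 days. The discontinuer sentence is the exception.

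**6. Effect on the overall rate, rare event.** Let T be the subject-years with the 84-day window and m the number of discontinuers. The subject-years omitted are m × 56 / 365.25, and the overstatement is T / (T − omitted) − 1.

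- Documented: Amendment 1 reports 460 enrolled and 432 still treated, so m = 28.
- Assumed: T from 1,800 to 2,600, and m = 250 as a high value.

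| m | Subject-years omitted | T = 1,800 | T = 2,600 |
|---|---|---|---|
| 28 | 4.3 | 0.24% | 0.17% |
| 250 | 38.3 | 2.18% | 1.50% |

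A constant-hazard simulation with an assumed 30% discontinuing uniformly over the dosing period gave rates 1.05%, 1.04% and 1.00% too high at hazards of 0.01, 0.05 and 0.2 per year. The effect falls as the event becomes more common.

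**7. Where it is larger.** For one event-free discontinuer with last dose at week w, the ratio of the two exposure times is (w + 12) / (w + 4): 38/30 = 1.27 at Week 26, 64/56 = 1.14 at Week 52 and 168/160 = 1.05 at Week 156. For a hypothetical column with a mean exposure of 1 year and 20% discontinuing, 0.2 × 0.153 / 1.0 is about 3%. The 300 mg dose is available only from Week 156, so its column has the shortest possible follow-up.

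**The case against.** **The denominator is set in 17.3.4.1, not in Section 10.** Neither section cites the other, and the undefined end of observation could be read as day 84, which would close the gap. This stands in part: the link is an inference. It is a strong one, because the rates are expressed per 100 subject-years of exposure, SAP Section 14 uses exposure start and stop dates for subjects who switch treatment, and Section 10 is the only place that defines a stop date.

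**Treatment period may mean the analysis period.** The SAP often uses the term that way, and then the last visit could be the follow-up visit. On that reading the discontinuer sentence adds nothing to the general rule, so it is the less likely one. Table 6-3 does print the discontinuation label in its Week 268 column while its footnote sends discontinuers to the end-of-period visit at 4 weeks. Those entries must be reconciled.

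**The size is easily overstated.** This stands. A reader might add the 606 − 460 = 146 core subjects who did not enter the extension to the 28 and treat 174 as discontinuers. The documents do not support this: the 146 may include core completers who declined or were judged not to benefit, and subjects who never received secukinumab. The core study's visit timing after stopping is also not in these documents. Fifty-six days is a maximum, reached only by an event-free subject who attends the 12-week visit. A reader might also infer that these subjects mostly stopped because of an adverse event, but no reasons are reported.

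**The effect matters little.** The analysis is descriptive, the error overstates risk, and with D = 100 the exact Poisson interval already runs from about −19% to +22% of the rate. That limits the importance of the point but does not justify mismatched windows.

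**Conclusion.** The mismatch is in the text: about 28 days of exposure against 84 days of event counting after last dose, for discontinuers only. If Section 10 supplies the denominator, the rates are biased upward. Under the assumed totals, the overstatement for rare events is at most about 0.2% with the 28 documented subjects and about 2% with an assumed 250. Neither the final number of discontinuers nor the total subject-years is in the documents. The 250 case also assumes the same visit timing for every discontinuer.

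The stronger statement, that the reported rates certainly omit 8 weeks for every discontinuer, goes beyond the documents while the censoring date in 17.3.4.1 is undefined. No safety conclusion is shown to change. The point merits correction because the change is cheap and the SAP must in any case say which end date governs the rates.

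**What to change.** 1. Delete the sentence on subjects who discontinue from SAP Section 10, so that the general rule applies to all.
2. In SAP 17.3.4.1, state that event-free subjects are censored at the earlier of last dose + 84 days and the last date of adverse event ascertainment, meaning the follow-up visit or a documented safety contact. Count treatment-emergent events over the same window.

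The first change alone leaves a gap: a discontinuer who misses the 12-week visit but is reached by telephone would still have exposure ended at the last visit while events were collected to day 84.

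The cost is one sentence removed and one added, with no new procedure for subjects. Rates become slightly lower. The Protocol asks for contact attempts to be recorded in source documents and does not say whether those dates reach the database, so their availability should be checked first.
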